WYZ Study Protocol

Study Title: A Mobile Health Application for Engagement in Care Among Youth Living With HIV

National Clinical Trial Number: NCT03587857

IRB Study Number: 16-20393

Date: 3/26/2019

WYZ Study Protocol

Contents

Protocol Title.....	2
Background	2
Objectives	3
Sample Size and Eligibility.....	4
Recruitment	4
Procedures.....	4
Outcome Measures.....	5
Data Analysis Plan.....	6
References	7

Protocol Title

WYZ: A Mobile Health Application for Engagement in Care Among Youth Living With HIV

Background

Globally, youth and young adults are recognized as being particularly vulnerable to HIV and bear a disproportionate share of the HIV burden, with HIV being the second leading cause of death.¹ In the USA, youth and young adults living with HIV (YLWH) have the lowest likelihood of linking to care, being retained in care, adhering to antiretroviral therapy (ART) and achieving viral suppression, compared with other age groups.²⁻⁴ One review estimated that among all YLWH in the USA, fewer than 6% are virally suppressed.⁵ The personal and public health consequences of suboptimal adherence among YLWH include poor health outcomes, increased drug resistance, reduced efficacy of existing treatment options, widening health disparities and potential transmission of drug-resistant virus. Efforts to adapt healthcare services for YLWH are critical, lest we risk a future generation of adults who are more susceptible to developing AIDS. While barriers to engagement in HIV care and ART adherence are generally similar across settings and populations, YLWH are more likely to report barriers such as forgetting, being away from home, change in daily routine, depression and alcohol and substance use compared with other age groups.⁶ Additionally, studies have shown that YLWH face many challenges across the HIV care continuum, and clinical outcomes are worse in this group compared with adults.⁷ The combination of these health disparities and developmental challenges in this transitional period may further hinder YLWH's ability to maintain optimal ART adherence and sustain virological suppression.^{1,7} The link between younger age and lower ART adherence and higher risk of

virological failure has been reported in numerous studies.^{8–11} However, there are few studies to inform the design of youth-friendly healthcare services and interventions.¹²

The widespread use of personal mobile phones presents an opportunity to develop novel interventions capable of bridging structural and systemic gaps in service and improving the equity of healthcare delivery. Mobile health (mHealth), the use of mobile technology for health, has the potential to reduce barriers to healthcare access, increase use of healthcare services and improve health outcomes among underserved populations.¹³ Reducing barriers like travel to healthcare settings, mHealth interventions hold the potential to increase accessibility for underserved populations and allow for more efficient use of provider resources.¹⁴ Additionally, technology-based interventions have the capacity to consistently deliver interventions with high fidelity and to complement and integrate with other healthcare services and technologies. As the largest consumers of mobile technology and internet use, youth and young adults hold the greatest potential to benefit from such technology-based interventions.¹⁵ In the USA, among 18–29 year-olds, greater than 77% download mobile applications and over 90% are users of social media.^{16 17}

There is a rapidly growing body of evidence demonstrating efficacy of mHealth interventions among various populations and for a variety of conditions, yet the field is nascent and confronting challenges related to limited generalisability,¹⁸ lack of rigorous long-term evaluations and demonstration projects,¹³ and complexities in evaluating efficacious theory-driven components.¹⁹ The purpose of our research is to build on our theory-guided model and formative research to develop an mHealth application called WYZ for improved engagement in HIV care and ART adherence, and pilot test it among 18–29 year-olds living with HIV.

Objectives

WYZ is an mHealth intervention designed and developed in collaboration with YLWH to improve ART adherence and engagement in HIV care among this age group. WYZ contains three main features, My Health, My Team, and My Community. My Health allows users to keep track of their ART medication information, visualize their adherence and laboratory data, and understand their health; My Team provides community resources and facilitates communication with health care team members; and My Community allows for social support from peers through anonymous and moderated discussion forums and allows users to stay up-to-date on health-related news. These features were developed with guidance from youth and young adults living with HIV and further refined through focus groups with youth and young adults living with HIV and iterative field testing with our Youth Advisory Panel (YAP), and were chosen to address specific barriers to ART adherence and engagement in HIV care (e.g., social isolation and lack of community support).

We will conduct a 6-month single-arm pilot study to examine WYZ feasibility and acceptability among YLWH (18–29 years old) who live or receive care in the San Francisco Bay Area. The objective of this forthcoming phase is to refine the design and development and pilot test WYZ.

All study activities, including recruitment, screening, enrolment, study assessments, provision of incentives and exit interviews, will be conducted remotely.

Sample Size and Eligibility

We will enroll up to 10 health care providers and up to 85 YLWH study participants. Of these 85, we will select a subset of 25 participants to take part in a 30 minute qualitative interview about their experience with the app.

Inclusion Criteria:

1. All YLWH will be confirmed HIV-positive, age 18-29, be able to speak and read in English, have a smartphone (iOS V10.0 and above or Android V5.0 and above), and be able to understand the consent procedure and voluntarily sign consent forms.
2. Health care providers are primary care providers, nurses, social workers and pharmacists who provide care to participating individuals.

Exclusion Criteria:

Those with evidence of severe cognitive impairment or active psychosis that impedes their ability to provide informed consent will be excluded.

Recruitment

A combination of recruitment strategies will be used to help achieve the study's enrolment goals. These include strategies such as posting flyers at clinics and community-based organizations, participant submission of contact information through the study website (wyz.ucsf.edu) and contacting healthcare team members to refer application users. We will also work with a city-wide consortium of youth service providers and the CAPS Youth Advisory Panel to disseminate study information to the target population. Enrolled participants will be encouraged to refer eligible peers and receive \$10 incentive for the referee and the referred individual who participates. Lastly, participants from the principal investigator's prior studies who had expressed interest and consented to be contacted about future research will be given the opportunity to participate, if still eligible.

Procedures

Eligibility screening

Interested individuals will be provided a brief overview of the study goals and given the chance to ask questions. Individuals wishing to enroll in the study will be screened for eligibility. To confirm an individual's age, we will require a photo identification showing their date of birth. To confirm an individual's HIV serostatus, we will require a clinician's letter of HIV diagnosis, copy of laboratory test results (for HIV antibody or HIV viral load), or the individual's ART prescription showing their name. These documents can be sent as a text message to the encrypted and secure study phone for verification by study staff.

Consent and enrollment

To enroll in the study, individuals will review and sign an electronic consent form sent to them via Qualtrics (Provo, UT, USA; version March 2017). All participants will be emailed a copy of the Experimental Subject's Bill of Rights as mandated by the State of California and a signed copy of their consent. If a participant does not have an email address, the study staff will assist them in signing up for one, as it will be necessary for gaining access to WYZ.

Participant retention

A number of steps will be taken to engage and retain participants throughout the study period. First, participants will be asked for multiple forms of contact information (including emergency contacts, clinical contacts and social media contacts) at the initial visit. They will receive monthly follow-up text messages to confirm that their contact information has not changed. Finally, participants will receive reminder text messages 24 hours before scheduled study activities.

Participant incentives

Participants can receive up to a total of \$215 incentive for completing all study activities. They will receive \$40 for the baseline session, which includes consent, application installation and baseline survey. They will then receive \$10, \$10, \$15, \$15, \$20, \$20 and \$25 for participating in check-ins at weeks 1, 2, 4, 8, 12, 16 and 20, respectively. For the final exit survey at week 24, participants will receive \$40, and those who are invited to participate in the exit qualitative interview at this time will receive an additional \$20. Part of this incentive is aimed at offsetting any data and text messaging fees associated with the application use. We estimate that participants will spend a total of 4–4.5 hours for study activities. Participants will be given a ClinCard, a reloadable debit card, which will be used for the remote provision of study incentives. Finally, we will offer \$50 to each healthcare provider for participating in a one-time qualitative interview.

Outcome Measures

The main outcomes of the pilot trial include feasibility and acceptability as indicated by meeting or exceeding the benchmarks presented in table 1. Feasibility will be assessed via user metrics by examining the participant's interactions with WYZ via a mobile analytics service called Flurry and backend (Salesforce) reporting tools (table 1). Acceptability will be examined during monthly check-ins to examine satisfaction with application use, the system usability scale (SUS),²⁰ a study-developed acceptability survey and an exit qualitative interview. HIV viral load and CD4+ cell count will be collected to determine feasibility of collecting these measures at both baseline and study completion.

Table 1

Feasibility metrics and threshold for determining feasibility

Measure	Threshold (per user)
General	
Recruitment	Recruit at least 55 participants (i.e., 70% of target n)
Number of log-ins	Mean of 1 log-in per week

Mean number of minutes in application	Mean of 15 min in application per week
My Health	
Use of refill feature	Use of feature once monthly (if receiving 30-day ART supply)
Use of ART adherence tracking	Track meds at least three times per week
Access of laboratory data	Review of laboratory data at least one time per month
My Team	
Communications with clinical team member	Mean of one communication per month with clinical team member
My Community	
Postchat or response to chats	Mean of one post or response to a post per week
Calendar and news	Minimum access once per week
Administrative	
Time for participant onboarding	Mean of 30 min to onboard (including downloading app and reviewing app features)
Time to maintain and support application	<1 hour per participant per week (excludes first visit)
Mean number of app crashes reported	Fewer than one self-reported app crash per week

Given that application use engagement is a complex and multifactorial concept, we aim to move beyond simple metrics. Therefore, in addition to feasibility measures detailed in table 1, we will examine an engagement index (EI) that has been detailed in other mHealth interventions.²¹ The EI includes the following subindices: (1) click depth (number of pages a user views per session), (2) loyalty (measures how frequently users access the application during the study period), (3) recency (the time difference between each session the user accessed the application), (4) interaction (number of push notifications opened from those sent through the application), and (5) feedback (subjective measure of participants' satisfaction with the application).

Data Analysis Plan

We have established minimum thresholds for determining the feasibility and acceptability of the intervention. Table 1 details these thresholds for the feasibility metrics. For acceptability, SUS scores range from 0 to 100 and scores >68 are considered above average. We will use a threshold of 70% or greater satisfaction to determine acceptability. Means and proportions will be computed at the study endpoint to enable descriptive evaluation of feasibility and acceptability. For EI, we will add all five subindices and examine cut-off points based on the distribution of the total samples' EI scores and categorize participants as either poorly, moderately or highly engaged.

On completion of the study, up to 20 participants will be invited to complete a one-time, audio-recorded semistructured qualitative exit interview with study staff by phone to further assess the acceptability of WYZ. We will select participants based on their EI category (i.e., poor, moderate or high engagement), and interviews will occur until data saturation or until 20 participants have been interviewed. The interviews will focus on the participant's (1) attitudes towards exiting features; (2) attitudes and perceptions of privacy and information security; (3) features that they would modify, add or eliminate; and (4) suggested modifications to increase engagement and sustained use of WYZ.

Finally, we will conduct in-depth qualitative interviews with clinical team members whose patients participated in the pilot study. The interview will focus on perceived (1) burden or ease of study procedures; (2) attitudes and beliefs regarding impact of the intervention on users' engagement in HIV care and ART adherence; (3) sustainability and scalability of the application to other youth in the clinic; (4) challenges of integrating an application into clinical work; and (5) suggested modifications to improve usability. All interviews will be done by phone, digitally recorded, transcribed verbatim and deidentified. Transcriptions will be analyzed using thematic and content analysis frameworks. This combination is useful in identifying implicit and explicit ideas within the data while also allowing for quantification of qualitative data.²²

References

1. Centers for Disease Control and Prevention. HIV and Youth: Viral Suppression. 2021; <https://www.cdc.gov/hiv/group/age/youth/viral-suppression.html>. Accessed March 9, 2022.

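### People who helped shape or test WYZ may enrol in the pilot, and no flag or analysis by prior involvement is described, so the single-arm benchmarks could be inflated without this being seen

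*Combined protocol and SAP*

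**What the plan says.** Objectives: WYZ was designed with young people living with HIV, and its features were "further refined through focus groups with youth and young adults living with HIV and iterative field testing with our Youth Advisory Panel (YAP".

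Sample Size and Eligibility: inclusion reads "All YLWH will be confirmed HIV-positive, age 18-29, be able to speak and read in English, have a smartphone", followed by the ability to understand and sign consent. The one exclusion is "Those with evidence of severe cognitive impairment or active psychosis that impedes their ability to provide informed consent will be excluded". Neither list mentions earlier contact with WYZ.

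Recruitment: "We will also work with a city-wide consortium of youth service providers and the CAPS Youth Advisory Panel to disseminate study information". In addition, "participants from the principal investigator's prior studies who had expressed interest and consented to be contacted about future research will be given the opportunity" to join, provided they still qualify. Enrolled participants are also paid to refer peers.

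Procedures, Eligibility screening: the documents requested verify age and HIV status only.

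Outcome Measures and Data Analysis Plan: the main outcomes are judged against fixed benchmarks. These are the use metrics in Table 1, a satisfaction threshold of 70%, and the System Usability Scale (SUS), where scores above 68 are called above average. The analysis consists of whole-sample means and proportions. No subgroup or sensitivity analysis by prior involvement is described.

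**The concern.** The pilot has one arm and no comparator, so its conclusion depends on whether observed figures reach preset levels. Someone who helped choose the features, or has already worked through versions of the app, may be more satisfied with it, find it easier to use and open it more often than someone meeting it for the first time. If so, including such people moves satisfaction, SUS and the use metrics towards a pass. With no marker in the data, a reader of the results could not tell how much of a pass came from contributors. Exit interviewees are chosen by engagement category, so the qualitative findings could be affected too.

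**Working it through.** **1. Do the rules allow it?** Focus-group members were young people living with HIV. Those aged 18–29 who speak and read English, own a suitable phone and can consent meet every listed criterion. The exclusion does not touch them, and the described screening steps would not identify them.

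**2. Inputs from the plan.** Maximum n = 85 (Sample Size and Eligibility); minimum recruitment n = 55 (Table 1); satisfaction threshold 70% (Data Analysis Plan). The threshold comes with no derivation or precision target, so there is no figure of the plan's own to reproduce.

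**3. Assumptions (none is given in the documents).** The threshold is a share of participants. Satisfaction among new users, p_new, is 60%, 65% or 68%; among contributors, p_con, it is 90% to 100%. The number of contributors, k, is 0, 5 or 10.

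**4. Count needed to pass.** 0.70 × 55 = 38.5, so 39 participants. 0.70 × 85 = 59.5, so 60 participants.

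**5. Expected share** = [(n − k) × p_new + k × p_con] / n. With p_new = 65% and k = 10:
- n = 55: (45 × 0.65 + 10 × 0.90)/55 = 38.25/55 = 69.5%; with p_con = 100%, 39.25/55 = 71.4%.
- n = 85: (75 × 0.65 + 10 × 0.90)/85 = 57.75/85 = 67.9%; with p_con = 100%, 58.75/85 = 69.1%.

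**6. Chance of observing at least 70%.** The number satisfied is the sum of Binomial(n − k, p_new) and Binomial(k, p_con), and the exact tail is taken at 39 or 60. Ranges run from p_con = 90% to 100%.

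| n | p_new | k = 0 | k = 5 | k = 10 |
|---|---|---|---|---|
| 55 | 60% | 6.3% | 12.8–15.6% | 23.4–32.7% |
| 55 | 65% | 22.0% | 33.6–38.9% | 47.7–59.8% |
| 55 | 68% | 38.1% | 50.8–56.7% | 63.8–75.2% |
| 85 | 60% | 2.8% | 5.5–6.7% | 10.2–14.4% |
| 85 | 65% | 16.7% | 24.6–28.2% | 34.4–43.3% |
| 85 | 68% | 35.1% | 44.9–49.6% | 55.4–64.9% |

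**7. Contributors needed for the expected share to reach 70%**: k ≥ n × (0.70 − p_new)/(p_con − p_new), rounded up, for p_con from 100% down to 90%.
- n = 55: 4–5 at p_new = 68%, 8–11 at 65%, 14–19 at 60%.
- n = 85: 6–8 at 68%, 13–17 at 65%, 22–29 at 60%.

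**8. Other benchmarks.** If ten contributors score 10 SUS points higher, the mean shifts by 10 × 10/55 = 1.8 points, or 10 × 10/85 = 1.2 points. For the Table 1 log-in benchmark (mean of 1 per week), suppose 50 new users average 0.8 per week. Five contributors at 2, 3 or 4 per week give (40 + 10)/55 = 0.91, (40 + 15)/55 = 1.00 or (40 + 20)/55 = 1.09.

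**The case against.** The strongest reply is that the documents do not place contributors in the sample. The Youth Advisory Panel is named as passing on information, not as a source of participants. It is not described as made up of people living with HIV, and that the panel in Objectives is the one in Recruitment is an inference, though a natural one. The prior studies are not said to include the WYZ focus groups. All of this stands. A reader might infer that contributors are known to be in the recruitment channels, but the text shows only that the rules would let them in.

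Second, the stated aim concerns young people living with HIV aged 18–29 and includes refining the app. The aim is not restricted to first-time users, so the all-participant figure is a legitimate answer to it. That stands too, and is a reason to report both figures rather than replace one.

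Third, the direction is assumed. Experienced testers could be more critical, or use a familiar app less. The documents do not settle this.

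Fourth, the baseline survey items are not listed, and staff who can recontact earlier participants may be able to match names later. It therefore goes too far to say that contributors could never be identified; the supported statement is that no flag is described.

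Fifth, a reader might infer that ten contributors among 55 turn a miss into a pass, since 65% and 95% satisfaction average to 70.5%. The expected count is 45 × 0.65 + 10 × 0.95 = 38.75 against 39 needed, and results vary around it. With 15 of 85 it is 70 × 0.65 + 15 × 0.95 = 59.75 against 60. Contributors raise the chance of a pass; they do not decide it.

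None of this removes the gap in the criteria and the analysis plan.

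**Conclusion.** The point holds as a modest, conditional one. Prior WYZ involvement is neither a criterion, nor a described screening item, nor an analysis factor. If contributors enrol and are more favourable than new users, the benchmarks could be inflated. At 65% satisfaction among new users, ten contributors at 90–100% would raise the chance of reaching 70% from about 22% to 48–60% at n = 55, and from about 17% to 34–43% at n = 85. The effect matters mainly when the true rate is just under 70% or contributors are a sizeable share of the sample. At a true rate of 60%, five contributors leave the chance of a pass at no more than about 16% (n = 55) or 7% (n = 85). The shift in mean SUS is small.

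These sizes rest on assumed rates and counts, and on reading the satisfaction threshold as a share of participants, which the Data Analysis Plan does not define. They illustrate what is possible and do not predict the result.

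**What to change.** Add one item at screening or in the baseline survey asking whether the person took part in WYZ focus groups or field testing. State in the Data Analysis Plan, before the data are examined, that the acceptability, SUS and use benchmarks will be reported for participants without prior WYZ involvement beside the all-participant figures, with the benchmark conclusion given for both. This shows a shift in either direction, and if few contributors enrol it shows that they hardly matter.

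The cost is one question, one extra table column and a slightly smaller denominator in that column. Excluding contributors is not needed, so recruitment is unaffected.

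### The recruitment benchmark is a total count with no accrual period, so meeting it does not separate brisk from slow recruitment.

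*Combined protocol and SAP*

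**What the plan says.** Outcome Measures defines the main outcomes as "feasibility and acceptability as indicated by meeting or exceeding the benchmarks presented in table 1". The first row of that table, under General, is "Recruit at least 55 participants", glossed there as 70% of the target.

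The only enrolment figure for young people living with HIV is in Sample Size and Eligibility: "We will enroll up to 10 health care providers and up to 85 YLWH study participants". The Recruitment section says "A combination of recruitment strategies will be used to help achieve the study's enrolment goals" and lists the sources: flyers, the study website, provider referral, a consortium of youth service providers and a youth panel, peer referral, and participants from prior studies. It gives no opening or closing date, no expected rate and no denominator.

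Objectives gives the only study duration: "We will conduct a 6-month single-arm pilot study to examine WYZ feasibility and acceptability among YLWH". Participant incentives places the exit survey at week 24. The Data Analysis Plan evaluates feasibility descriptively at the study endpoint, without a calendar date.

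**The concern.** The rule has one input, the number of participants recruited. Time does not enter it, nor does the number of people who were offered the study. A pilot that fills quickly and one that takes several times as long receive the same result if both end at 55 or more.

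The other parts of Table 1 show that a rate was within reach. The eight usage rows (log-ins, minutes, refill, adherence tracking, laboratory data, communications, posts, calendar and news) each carry a weekly or monthly unit. Recruitment carries none.

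What is at stake is the meaning of a pass. Recruitment is one of the benchmarks by which feasibility is declared, and a reader would take a pass as evidence that these young people can be recruited at a workable pace. The rule as written does not test pace. A window chosen once accrual has been seen would not repair this, because it could be chosen to fit.

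**Working it through.** **1. The plan's own figure.** Inputs: threshold 55 and 70% (Table 1); target up to 85 (Sample Size and Eligibility).

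- 0.70 × 85 = 59.5, so 60 participants.
- 55 / 85 = 64.7%.
- 55 / 0.70 = 78.6, so 55 would be 70% of a target of 78 or 79, which the documents do not state.

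The threshold therefore does not reproduce from the stated target.

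**2. Do the six months supply a window?** The exit survey is at week 24, and 24 × 7 / 30.44 = 5.5 months, so six months matches one participant's follow-up. If six months (about 26 weeks) also had to contain accrual, everyone would have to enrol in roughly the first 26 − 24 = 2 weeks. No section says so.

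**3. How the count behaves over time.** The documents give no accrual rate, so the rates below are assumptions. With Poisson accrual at rate r per month, the number enrolled by month T is Poisson with mean rT. Then P(at least 55) = 1 − F(54; rT), where F is the Poisson distribution function, and the expected time to the 55th participant is 55 / r.

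| Assumed rate per month | Expected months to 55 | P by month 12 | P by month 18 | P by month 24 | P by month 36 |
|---|---|---|---|---|---|
| 2 | 27.5 | about 0% | 0.2% | 17% | 98% |
| 3 | 18.3 | 0.2% | 46% | 98% | about 100% |
| 5 | 11.0 | 76% | about 100% | about 100% | about 100% |

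Down a column (window fixed), the row discriminates: at 12 months, 76% against 0.2% for 5 and 3 per month. Along a line (window extended), the difference disappears: 3 per month is very unlikely to pass at 12 months and very likely to pass at 24.

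**4. What a window would require.** The average rate needed is N / X.

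| Assumed window X (months) | N = 55 | N = 60 |
|---|---|---|
| 6 | 9.2 per month | 10.0 per month |
| 12 | 4.6 | 5.0 |
| 18 | 3.1 | 3.3 |
| 24 | 2.3 | 2.5 |

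The choice of X moves the required rate about fourfold over this range (9.2 / 2.3 = 4.0). The choice between 55 and 60 moves it by 60 / 55, about 9%.

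**The case against.** The natural reading of the row is the share of the target reached when enrolment closes. On that reading a shortfall is informative, and reporting enrolment dates with the result would remove much of the ambiguity of a pass. The benchmarks are descriptive, recruitment is one of 12 rows, and no section names a later, larger trial against which the row should be judged. All of this stands, and it limits the point to what a pass means.

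A reader might infer more. One inference is that 55 is a stopping target, with enrolment kept open until it is reached. The documents do not say this: 55 is a floor beneath "up to 85 YLWH study participants", and nothing states that enrolment stops at 55 or continues until 55. Another is that any positive enrolment rate would eventually pass. That needs unlimited time and an eligible pool that is not exhausted, whereas the study is limited to smartphone-owning English speakers aged 18–29 who live or receive care in one metropolitan area. A third is that the row can say nothing about feasibility, which the informative shortfall contradicts.

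The objection does not remove the gap itself. Funding or staffing may well end accrual, but no such limit is written. A limit outside the protocol can be moved after accrual is seen. Dates reported afterwards describe the pace without testing it against a criterion fixed in advance.

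**Conclusion.** The point holds in a limited form. The recruitment row is a complete rule on a bare count, with no accrual period in the row or elsewhere, so a pass does not distinguish brisk from slow recruitment. The size shown is illustrative: at an assumed 3 per month, the chance of meeting the row goes from 0.2% to 98% when the window goes from 12 to 24 months. It rests on constant Poisson rates that the documents do not give, and it describes how the rule behaves. It does not predict this trial's accrual.

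A smaller discrepancy sits in the same row: 55 and 70% do not agree with a target of 85.

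**What to change.** Before first enrolment, restate the row as: *at least N participants enrolled within X months of opening enrolment*. The sponsor should set X from its planned accrual period, since the documents contain no timeline from which to take it.

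- Judge the row at month X, even if enrolment then continues.
- Report the number enrolled per month, and enrolled out of screened eligible, by recruitment source where known. Note beside the proportion that screening applies to people who already wish to enrol, so it measures conversion among a self-selected group and not uptake among all who were reached. With flyers, a website and peer referral, the number reached would be hard to count.
- Reconcile N with the target in the same edit: keep 70% of 85 and use 60, keep 55 and describe it as 64.7% of 85, or state the different target from which 55 was derived.

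The cost is one row of wording and a dated count of those screened, eligible and enrolled, with source. The documents describe eligibility screening but no log of it, so that count would need to be kept. No extra participants or study visits are needed. The downside is that the row may be missed although the pilot later reaches N; if so, both facts should be reported.

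### Does the 70% satisfaction mark leave the acceptability verdict open, because two sections point to different rules and the summary statistic is not named?

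*Combined protocol and SAP*

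**What the plan says.** Outcome Measures opens with "The main outcomes of the pilot trial include feasibility and acceptability as indicated by meeting or exceeding the benchmarks presented in table 1". It then takes the two outcomes one at a time. Feasibility is assessed from user metrics, with a reference to Table 1. For acceptability it says "Acceptability will be examined during monthly check-ins to examine satisfaction with application use", and it adds the SUS, a study-developed survey and an exit interview. Table 1 is titled "Feasibility metrics and threshold for determining feasibility".

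The Data Analysis Plan says "Table 1 details these thresholds for the feasibility metrics". It turns to acceptability with "For acceptability, SUS scores range from 0 to 100 and scores >68 are considered above average", followed by the pass mark: "We will use a threshold of 70% or greater satisfaction to determine acceptability". The next sentence is "Means and proportions will be computed at the study endpoint to enable descriptive evaluation of feasibility and acceptability".

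Satisfaction is also mentioned in the engagement index, whose feedback subindex is a "subjective measure of participants' satisfaction with the application". Participant incentives places a final exit survey at week 24.

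**The concern.** Acceptability is one of two main outcomes and has a preset mark. Two features suggest that the mark does not settle the verdict.

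- **Two apparent rules.** Taken alone, the opening clause of Outcome Measures judges acceptability by Table 1, while the Data Analysis Plan judges it by satisfaction. A study that met its usage benchmarks with satisfaction below 70% would be acceptable under one and not under the other.
- **One mark, two summaries.** Means and proportions are both to be computed, and 70% is attached to neither. Satisfaction could come from the check-ins, the study's own survey or the engagement index. The SUS value of 68 could be a reference point or a second benchmark.

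With no control arm, comparison with the preset mark carries weight. If the summary or instrument were chosen after the ratings were seen, the comparison would lose its value even with no data missing.

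**Working it through.** **Which rule applies.** The Table 1 rows are 3 general + 3 My Health + 1 My Team + 2 My Community + 3 administrative = 12. They cover recruitment, use, onboarding, support time and crashes. Acceptability rows: 0. Acceptability therefore cannot be read off Table 1. The two sentences after the opening clause, the table title and the Data Analysis Plan all assign the table to feasibility. Only the 70% mark is left as an acceptability rule.

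**Can mean and proportion disagree?** The 70% is set by decision, so there is no derived figure to reproduce. From the documents: up to 85 participants, and 55 as the recruitment benchmark. A proportion rule needs 0.70 × 85 = 59.5, so 60 of 85, or 0.70 × 55 = 38.5, so 39 of 55. The scales and distributions below are assumptions.

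*Five-point item, 4 or 5 counted as satisfied, n = 55: 41 rate 4 and 14 rate 2.*
- Proportion: 41/55 = 74.5%, pass.
- Mean: (41×4 + 14×2)/55 = 192/55 = 3.491. Rescaled: (3.491 − 1)/4 = 62.3%, fail.

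*0-100 score, 60% at 90 and 40% at 50.*
- Mean: 0.6×90 + 0.4×50 = 74.0, pass.
- Share at 70 or above: 60%, fail.

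*Normal scores with mean 72.* The share at 70 or above is Φ(2/SD): 57.9%, 55.3% and 54.0% for SD 10, 15 and 20. The mean passes and the proportion fails each time. For 70% of users to score at least 70, the mean must be 70 + 0.524×SD, which is 75.2, 77.9 or 80.5.

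Disagreement is therefore possible in both directions.

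**A less extreme case.** Take 85 ratings of 5/4/3/2/1 = 17/36/24/6/2.
- Proportion: 53/85 = 62.4%, fail.
- Mean: (85 + 144 + 72 + 12 + 2)/85 = 315/85 = 3.706. Rescaled: 2.706/4 = 67.6%, fail.
- Mean over maximum: 3.706/5 = 74.1%, pass.

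Only the third passes. The documents mention no such conversion, and it credits the worst rating, 1 of 5, with 20%. If this were the true distribution, the proportion would pass in 7% of samples of 85 and the rescaled mean in 19%. In simulation (400,000 draws) the two gave the same verdict in 86% of samples at n = 85 and 84% at n = 55.

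**What a reader would see.** The plan commits to both types of summary at the study endpoint. If they fell on opposite sides of 70%, the report could show it.

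**The case for a change.** The strongest opposing case sets the clause about Table 1 aside. A pass mark should be determinate before results are seen, and this one is not. Several Table 1 rows name their statistic, such as a mean of one log-in per week, so the plan could have done the same here. The text says minimum thresholds have been established, and one added sentence would close the gap at almost no cost.

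Much of this stands. The instrument, the summary and the cut for satisfied are not written down, and the verdict can differ on complete data. Stating them would be good practice.

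Three points limit its weight. First, 70% or greater satisfaction reads most naturally as a share of participants, while the SUS and several Table 1 benchmarks are naturally means. One sentence announcing both summaries for both outcomes is consistent with that. Second, the engagement index is a weak rival source: it serves to group participants by engagement and is not among the acceptability sources in Outcome Measures. Third, the item wording and scale belong to a study-developed survey that the documents do not reproduce, so a replacement sentence written from the documents alone would have to leave the item blank.

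**Conclusion.** No change to the plan is needed. The pointer from acceptability to Table 1 is a clerical slip that the surrounding text corrects, and it does not create a second rule. The unnamed summary and instrument are a gap that analysts can fill sensibly: report the share satisfied at the endpoint against 70%, give the mean beside it, and report the SUS on its own scale.

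Followed as written, the plan produces no wrong result. The evaluation is descriptive, no type I error or power is affected, and acceptability also draws on exit interviews.

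How far mean and proportion would diverge is unknown. The constructed examples and the normal model show that opposite verdicts can occur. The five-point example with 85 ratings shows the proportion and the rescaled mean agreeing in about 85% of samples. All of these figures rest on assumed scales, cuts and distributions. The conclusion would be different if a test or a stated go/no-go decision depended on the mark, or if only one summary were to be reported.
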